AST and/or ALT baseline G0 → G1 or baseline G1 → G2	Treat on time and check AST, ALT and bilirubin 2x/week for 2 weeks followed by weekly assessments for at least 4 weeks.		Treat on time and check AST, ALT and bilirubin 2x/week for 2 weeks followed by weekly assessments for at least 4 weeks.
AST and/or ALT baseline G0 → G2	Delay until ≤ G1 and check AST, ALT, bilirubin 2x/week.	Reduce 1 dose level and check AST, ALT, bilirubin 2x/week for 2 weeks followed by weekly assessments for at least 4 weeks. ^a	Discontinue ^b
AST and/or ALT baseline any grade → G3	Delay until ≤ G1 if baseline was G0 or G1 OR until G2 if baseline was G2. Check AST, ALT, bilirubin 2x/week. If ALT or AST > 8 x ULN with a concomitant rise in bilirubin (of any degree) compared to previous bilirubin values, consider permanent discontinuation at the first occurrence ^b .	Reduce 1 dose level and check AST, ALT, bilirubin 2x/week for 2 weeks followed by weekly assessments for at least 4 weeks. ^a	Discontinue ^b
AST and/or ALT baseline any grade → G4	Discontinue ^b		

Abbreviations: AST = aspartate aminotransferase, ALT = alanine aminotransferase
 
^a If all values remain stable for 2 full cycles, dose re-escalation may be considered at the discretion of the investigator. After re-escalation AST, ALT, bilirubin should be checked 2x/week for 2 weeks, followed by weekly assessments for at least 4 weeks.
 
^b In case of discontinuation, check AST, ALT, bilirubin should be checked twice a week for 2 weeks, followed by weekly assessments until recovery to baseline.
			

During the first 2 cycles of treatment, ALT, AST and bilirubin must be monitored weekly.

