7.1 Schedule of procedures

Please see study schedule, Table 7.

- Patients will be seen by physician every week for the first cycle, every two weeks for the second cycle, at the start of each cycle after this, and at end of treatment.
- Assessment of concomitant medications at the start and during each visit.
- ECOG testing at start of treatment, at the start of physician visit and at the end of treatment.
- Blood pressure will be measured every week for the first cycle, on day 1, 7, and 14 in the second cycle, at the start of each cycle after this, and at follow up visit.
- Liver function tests [albumin, bilirubin (total), bilirubin (direct), alkaline phosphatase, GGT, AST, LDH] will be administered every week for the first cycle, every two weeks for the second cycle, at the start of each cycle after this, and at follow up visit.
- Lipase testing, electrolytes, TSH, chemistry, CEA testing, CBC, and creatinine will be done at D1 of each cycle and at end of treatment.
- A twelve-point ECG will be administered on D1 of each cycle and at the end of treatment.
- Other tests will be administered as per standard of care for regorafenib and perindopril.

The study protocol will include a patient education module. This will consist of a patient education brochure regarding the management of HFSR and will include the preventative measures patients can take to manage this side effect.

Patients will have photos of hands and feet taken at BCCA media services for illustrative purposes only, on Day 1, Day 7, Day 14 and Day 21 of the first cycle only. A total of about eight photographs per visit will be taken to capture the dorsal and plantar sides of the patient's hands and feet. The digital photographs will be labeled with your participant study number and the date. A digital copy of each photograph will be stored in the Cancer Agency Information System and a hardcopy stored in the subject study file. All photographs for the subject's study folder are to be printed with images approximately 6.25 x 9 inches on 8.5 x 11 photo paper. All photos need to be identified with study ID number and date taken.

Phase II Study of Perindopril and Regorafenib in mCRC (PARICCA)

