7.1.1 Tabulated overview

Table 7

Procedure	Day -28 to Day -1	Day -14 to Day -1	Day -7 to Day -1	Cycle 1				Cycle 2				Cycle 3+	End of treatment	Follow up (+1 month)
				Day1	Day7	Day14	Day21	Day1	Day7	Day14	Day21			
Medical History	x												x	
Physician Visit		x		x	x	x	x	x		x		x	x	
Concomitant Meds.		x		x	x	x	x	x	x	x		x	x	x
ECOG		x		x	x	x	x	x		x		x	x	
Blood Pressure		x		x	x	x	x	x	x	x		x	x	
Liver Function Tests			x	x	x	x	x	x		x		x	x	
12-lead ECG	x			x				x				x	x	
Cardiac Function Test*				x ¹				x ¹				x ¹		
Lipase Testing			x	x [#]				x				x	x	
PT or PT-INR and PTT			x	x [#]				x				x	x	
Full urinalysis, measure of proteinuria and GFR			x	x [#]				x				x	x	
AE				x	x	x	x	x	x	x		x	x	x
CEA			x	x [#]				x				x	x	
CBC			x	x [#]				x				x	x	
Creatinine			x	x [#]				x				x	x	
Electrolytes			x	x [#]				x				x	x	
TSH			x	x [#]				x				x	x	
Chemistry			x	x [#]				x				x	x	
hCG			x											
CT - every eight weeks	x			x								x		
Photos				x	x	x	x							

Lipase, Creatinine, Electrolytes are generally inclusive with chemistry.

34 patients, Study expected to last 2 -4 cycles

Tests will be administered as per standard of care for Regorafenib

PROTOCOL Version 2.2 Dated 08 February 2017

Phase II Study of Perindopril and Regorafenib in mCRC (PARICCA)

Weekly monitoring by physician in first cycle

* Echocardiogram or MUGA scan

¹ Echocardiogram or MUGA scan only if clinically indicated. Echocardiograms or MUGA scans should be performed by the same operator to minimize inter-observer variability.

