Phase II Study of Perindopril and Regorafenib in mCRC (PARICCA)

- Record of all concomitant prescribed and over-the-counter medications. All medications and significant non-drug therapies taken within 14 days before study treatment must be recorded in the CRF.

The following procedures and assessments will be performed **within 7 days of starting study drug**:

- A CBC with differential should be performed: RBC, hemoglobin, hematocrit, platelet count and WBC. WBC must include differential neutrophil, lymphocyte, monocyte, basophil and eosinophil counts.
- Electrolyte panel: sodium, potassium, chloride and Chemistry panel: Aspartate Amino-Transferase (AST), bilirubin (total and direct), Gamma GT, alkaline phosphatase, total protein, albumin, calcium, lipase, amylase, phosphate, Lactic Dehydrogenase (LDH), glucose, creatinine and Blood Urea Nitrogen (BUN).
- Thyroid function test (TSH, free T3, free T4).
- Coagulation panel: Prothrombin time (PT) or the International Ratio of PT (PT-INR) and Partial Thromboplastin Time (PTT).
- Urinalysis: appearance, pH, glucose, ketones, erythrocytes, leukocyte esterase, nitrite, bilirubin, urobilinogen, protein, creatinine, and protein/creatinine ratio. A microscopic analysis should be performed if the appearance is turbid, or if protein, leukocytes, erythrocytes or nitrite are out of normal range.
- Quantification of proteinuria by urinary protein/creatinine ratio (UPCR) on a random urine sample preferably taken at mid-morning. This should be reported as the ratio of concentrations of total urine protein (in mg/dl) to urine creatinine (in g/dl). If UPCR is outside of Normal Range (>30 g/mol Creat), then a 24-hour urine protein test should be performed to confirm Grade 3 or higher proteinuria (>3.5 g/24 hours).
- Measurement of GFR according to the MDRD (Modified diet in renal disease) abbreviated formula.
- Carcinoembryonic antigen (CEA) testing.
- A negative urine or serum pregnancy test for women of childbearing potential.
- The inclusion and exclusion criteria should be checked during the screening period to ensure appropriate patients are enrolled.

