7.1.2.2 Treatment

The following assessments should be performed on the **first day of each cycle** (every 4 weeks) prior to receiving study treatment (+/- 7 days):

- The inclusion and exclusion criteria should be checked to ensure appropriate patients are treated at Day 1 of Cycle 1 only.
- Physical examination including vital signs (pulse and blood pressure), weight, temperature and examination of pertinent organ systems ECOG performance status

Phase II Study of Perindopril and Regorafenib in mCRC (PARICCA)

- Toxicity and adverse events documentation (including Start/Stop dates, seriousness, CTC notation and grading, relationship to study drug, outcome and action taken) using CTCAE v4.03
- Concomitant medications (including start/stop dates, dose, indication)
- Echocardiogram or MUGA scan only if clinically indicated. Echocardiograms or MUGA scans should be performed by the same operator to minimize inter-observer variability.

The following laboratory evaluations are not required at Day 1 of Cycle 1 if these were completed within 7 days of starting study drug treatment. Otherwise, these laboratory evaluations are required on Day 1 of each cycle:

- CBC with differential should be performed: RBC, hemoglobin, hematocrit, platelet count and WBC. WBC must include differential neutrophil, lymphocyte, monocyte, basophil and eosinophil counts. (note: BCCA lab does 5 part differentials).
- Electrolyte panel: sodium, potassium, chloride and Chemistry panel: Aspartate Amino-Transferase (AST), bilirubin (total and direct), alkaline phosphatase, triglyceride levels, uric acid, total protein, albumin, calcium, lipase, amylase, phosphate, Lactic Dehydrogenase (LDH), glucose, creatinine and Blood Urea Nitrogen (BUN)
- Thyroid function test (TSH, free T3, free T4)
- Coagulation panel: Prothrombin time (PT) or the International Ratio of PT (PT-INR) and Partial Thromboplastin Time (PTT). If a patient is on warfarin with stable PT/INR at baseline, the PT/INR should be assessed on Day 5 of Cycle 1. If either of these values is above the acceptable range, the doses should be modified and the assessments should be repeated weekly until it is stable.
- Urinalysis: appearance, pH, glucose, ketones, erythrocytes, leukocyte esterase, nitrite, bilirubin, urobilinogen, protein, creatinine, and protein/creatinine ratio. A microscopic analysis should be performed if the appearance is turbid, or if protein, leukocytes, erythrocytes or nitrite are out of normal range.

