The following assessments should be performed on **day 7 of the second cycle** (+/- 3 days):

- Blood pressure
- Assessment of AEs
- Concomitant medications

The following assessments should be performed on **day 14 of the second cycle** (+/- 3 days):

- Physician visit
- ECOG status
- Liver function tests
- Assessment of AEs
- Concomitant medications
- Blood pressure

Tumor measurements (CT/MRI scans) will be conducted every 8 weeks. A PET scan is not acceptable for radiological evaluation. Throughout the study, the identical lesions to those identified and measured at baseline must be evaluated using the same technique, and preferably by the same investigator/radiologist. MRI/CT scans must meet the standard of care for the imaging of lesions in the respective organ system(s). Copies of all imaging (CT scans, MRI, X-rays, ultrasound, photographs of cutaneous lesions, etc.) performed for tumor assessment in all enrolled patients will be stored electronically at the site.

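### Weekly ALT, AST and bilirubin testing is mandatory for two cycles, but the schedule tests only twice in cycle 2 and no itemised laboratory panel names ALT

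*Combined protocol and SAP*

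**What the plan says.** **Frequency.** The sentence after Table 6 in Section 6.4.2 reads: "During the first 2 cycles of treatment, ALT, AST and bilirubin must be monitored weekly". Section 7.1 reads: "Liver function tests [albumin, bilirubin (total), bilirubin (direct), alkaline phosphatase, GGT, AST, LDH] will be administered every week for the first cycle, every two weeks" in the second cycle, then at the start of each later cycle and at the follow-up visit. In Table 7 the row "Liver Function Tests" is marked on Days 1, 7, 14 and 21 of cycle 1, on Days 1 and 14 of cycle 2, at cycle 3 onwards and at end of treatment. In Section 7.1.2.2 the list for "day 7 of the second cycle" has blood pressure, adverse events and concomitant medications only. The list for "day 14 of the second cycle" includes liver function tests. There is no list for Day 21 of cycle 2, and Table 7 has no procedure of any kind on that day.

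**Analytes.** Three places itemise what is measured: the bracketed list in Section 7.1 quoted above; the screening panel in Section 7.1.2.1, "Chemistry panel: Aspartate Amino-Transferase (AST), bilirubin (total and direct), Gamma GT, alkaline phosphatase, total protein, albumin" and further items; and the panel for Day 1 of each cycle in Section 7.1.2.2, "Chemistry panel: Aspartate Amino-Transferase (AST), bilirubin (total and direct), alkaline phosphatase, triglyceride levels, uric acid" and further items. None of the three, read to its end, includes ALT. Section 5.1.1 sets an eligibility limit on both ALT and AST, and all four rows of Table 6 are written for AST and/or ALT.

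**Follow-up visit.** Table 7 leaves the follow-up column blank for liver tests. Section 7.1.2.4 asks only for concomitant medications and adverse events and allows the contact to be by telephone.

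**The concern.** The dosing section makes a liver check mandatory, and the section that staff use to book visits and order tests does not provide for it. A site that follows Table 7 and the visit lists to the letter would comply with Section 7 and breach Section 6.4.2 in cycle 2.

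The missing analyte adds to this. From the listed panels alone, the ALT half of the eligibility limit could not be checked. Nor could the ALT half of Table 6 be applied, including its clause on values above 8 times the upper limit of normal. Three of the four rows of Table 6 also turn on the baseline grade, so a screening panel without ALT leaves the ALT baseline undefined.

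The subject is not peripheral. Section 7.5.1.5 (Expected adverse events) puts severe liver injury among the most serious regorafenib reactions, and Section 1.2 reports raised ALT in the CONCUR trial in 31.6% of patients at any grade and 8.1% at grade 3. Purely as illustration, if those rates applied to 34 patients they would mean 0.316 × 34 ≈ 11 and 0.081 × 34 ≈ 3 patients.

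**Working it through.** The plan gives no figure to reproduce here. The check compares the provisions and counts test days.

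**Step 1: cycle 2 provisions side by side**

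| Place | Liver tests in cycle 2 |
|---|---|
| Section 6.4.2, below Table 6 | Weekly |
| Section 7.1 | Every two weeks |
| Table 7 | Days 1 and 14 |
| Section 7.1.2.2 visit lists | Day 14 yes; Day 7 no; no Day 21 list |

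The last three agree with one another and differ from the first. Prose and table say the same thing, so a badly extracted table cannot explain the conflict.

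**Step 2: number of checks.** On the schedule's own visit days (1, 7, 14, 21), weekly testing over two cycles means 4 + 4 = 8 checks. The schedule provides 4 + 2 = 6. The two missing are Days 7 and 21 of cycle 2.

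**Step 3: nominal gaps.** With 28-day cycles, cycle 2 Day 1 is study day 29, cycle 2 Day 14 is 28 + 14 = 42, and cycle 3 Day 1 is 57.
- Day 1 to Day 14 of cycle 2: 42 − 29 = 13 days.
- Cycle 2 Day 14 to cycle 3 Day 1: 57 − 42 = 15 days.
- Under a weekly rule: 7 days.

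**Step 4: effect of visit windows.** Section 7.1.2.2 allows ±3 days on Day 14.
- A late Day 14 stretches the first gap to 13 + 3 = 16 days; an early one stretches the second to 15 + 3 = 18. Both cannot happen in the same patient.
- Section 7.1.2.2 gives ±7 days for its first list of Day 1 assessments and does not repeat it for the laboratory list. If it is assumed to cover the laboratory tests, and Day 14 keeps its planned date, the extremes are 16 + 7 = 23 or 18 + 7 = 25 days.
- A weekly grid with the same windows (assuming ±3 days on Day 21) would also stretch: 7 + 3 + 3 = 13 days between interim visits, and 8 + 3 + 7 = 18 days from Day 21 to the next Day 1. Like for like, the worst case is 18 against 13 days without the Day 1 window and 25 against 18 with it.

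**Step 5: cohort total.** If 34 patients are treated and all complete cycle 2, 2 × 34 = 68 checks required by Section 6.4.2 have no place in the schedule. If all 38 recruited patients were dosed and completed cycle 2, the figure would be 2 × 38 = 76.

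**Step 6: analytes**

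| Itemised panel | AST | Bilirubin | ALT |
|---|---|---|---|
| Section 7.1 liver function tests | Yes | Yes | No |
| Section 7.1.2.1 screening chemistry | Yes | Yes | No |
| Section 7.1.2.2 Day 1 chemistry | Yes | Yes | No |

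AST and bilirubin appear in 3 of 3 panels and ALT in 0 of 3.

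**Step 7: can another clause fill the gap?** Section 7.1 and the notes to Table 7 fall back on standard of care ("Tests will be administered as per standard of care for Regorafenib"). Neither clause names ALT or a frequency, and Section 7.1 defines liver function tests by an explicit list. The more frequent checks in Table 6 do name ALT, but they start only once a rise has been found.

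**The case against.** The strongest reply is that both rules can be obeyed together. Section 6.4.2 is as binding as Section 7, and Section 11.1 demands strict adherence to everything in the protocol. Weekly testing also satisfies a two-weekly schedule, and nothing forbids measuring ALT. Section 5.1.1 itself calls for ALT within 7 days before treatment, and eligibility is checked at screening and again on Day 1 of cycle 1, so a missing ALT should come to light before dosing. The AST and bilirubin parts of the rules can be applied from the listed panels in any case.

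Much of this stands. ALT may well be measured in practice, and the fault lies in the schedule and the panels, not in site conduct. It does not remove the contradiction. A mandatory test with no visit, and a decision rule whose analyte is not on the order list, both depend on staff noticing the mismatch.

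It is also fair that the windowed gaps should not be set against a bare 7 days, and that the cohort total depends on how many patients are dosed and complete cycle 2. The firm figures are the 2 of 4 checks and the nominal 13 and 15 days. The follow-up mismatch is minor: Section 7.1 uses the same phrase for blood pressure, which Table 7 likewise does not mark at follow-up, so it looks like a general wording slip.

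**Conclusion.** The inconsistency is real in the current text. In cycle 2 the schedule provides 2 of the 4 weekly checks that Section 6.4.2 requires (6 of 8 over two cycles), with nominal gaps of 13 and 15 days against 7. ALT is in none of the three itemised panels although the eligibility limit and every row of Table 6 use it. The follow-up visit mismatch is a lesser third point.

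The counts rest on the visit days in Table 7 and need no outside figure. Only the windowed gaps and the cohort totals depend on the assumptions stated with them. The log in Section 13 suggests the origin: version 1.2 dropped the liver tests from cycle 2 Day 7 because no physician visit is scheduled then, and the weekly sentence was not brought into line. The finding does not rest on the log.

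This should be fixed because it concerns safety monitoring. It does not touch the primary HFSR comparison, the sample size or the interim stopping rule.

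**What to change.** 1. Reconcile the weekly sentence in Section 6.4.2 with Section 7.1, Table 7 and the cycle 2 visit lists in Section 7.1.2.2, so that one monitoring frequency applies throughout. Which frequency is right is for the sponsor to decide.
2. Reconcile the three itemised panels with Section 5.1.1 and Table 6, so that panels and rules name the same analytes.
3. Reconcile the follow-up wording in Section 7.1 with Table 7 and Section 7.1.2.4.

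**Cost.** Protocol wording, plus one analyte on blood already drawn if the panels are aligned with the eligibility limit and Table 6. If the two-weekly schedule is kept, no further draws. If the weekly rule is kept, up to two further draws per patient in cycle 2, on Days 7 and 21. Day 7 has no physician visit and Day 21 has no procedure at all, so each may need an added clinic or laboratory attendance.

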6.5 Blinding

N/A All patients in the study will receive both regorafenib and perindopril.

6.6 Drug logistics and accountability

All study drugs will be stored at the investigational site in accordance with GCP and GMP requirements. Study supply of regorafenib, along with storage and handling instructions will be provided by Bayer HealthCare. Perindopril, including its storage and handling instructions will be obtained by the sponsors from the market. Both study drugs will be inaccessible to unauthorized personnel.

Special storage conditions and a complete record of batch numbers and expiry dates can be found in the study file; the site-relevant elements of this information will be available in the investigator site file. The responsible site personnel will confirm receipt of study drug and will use the study drug only within the framework of this clinical study and in accordance with this protocol. Receipt, distribution, return and destruction (if any) of the study drug must be properly documented according to BCCA specified procedures. Written instructions on medication destruction will be made available to affected parties as applicable.

To have complete control over the distribution and use of the study drug, the drug accountability must be performed on Day 1 of each cycle starting on Cycle 2. Bottles must be returned to the Investigator with all unused medication. Throughout the study, all unused study medication will be accounted for. The information will be recorded in the drug dispensing log, as per BCCA protocol.

6.7 Treatment compliance

An adequate record of the receipt, distribution and return of all study medication supplies must be recorded on the Drug Accountability Form. The number of tablets dispensed and returned by the patients will be recorded in the drug accountability logs in the CRF.

Drug accountability must be done at every cycle, starting on Day 1 of Cycle 2.

The dose and schedule of regorafenib and perindopril administered to each subject will be recorded in the CRF. The reason(s) for dose delay, reduction or interruption also will be recorded in the CRF.

6.8 Post-study therapy

All subjects will enter the follow-up period upon discontinuation of study treatment. Regardless of the reason for discontinuation all subjects will be followed for survival until death is

documented, except for those who specifically withdraw consent to follow-up. Subjects who withdraw consent from study drug treatment may enter the Follow-up Period.

6.9 Prior and concomitant therapy

All medication which is considered necessary for the subject's welfare, and which is not expected to interfere with the evaluation of the study drug, may be given at the discretion of the Investigator (except strong CYP3A4 inhibitors/inducers [see Appendix 14.7 and 14.8]).

All concomitant medications (including start/stop dates, dose frequency, route of administration and indication) must be recorded in the patient's source documentation, as well as in the appropriate pages of the CRF. Specific caution should be employed when considering or administering a concomitant medication that is metabolized by the cytochrome enzymes CYP2C8, CYP2B6 and CYP2C9 or the Phase II glucuronosyl transferases UGT1A1 and 1A9. Such concomitant medications should be avoided, if possible.

Concomitant administration of ketoconazole, a strong CYP3A4 inhibitor, with regorafenib resulted in an increase in mean exposure (AUC) of regorafenib of approximately 33%, and a decrease in mean exposure of the active metabolites, M-2 (N-oxide) and M-5 (N-oxide and N-desmethyl), of approximately 90%. It is recommended to **avoid concomitant use of strong inhibitors of CYP3A4 activity** (e.g. clarithromycin, grapefruit juice, itraconazole, ketoconazole) as their influence on the steady-state exposure of regorafenib and its metabolites has not been studied. (See Appendix 14.7)

Concomitant administration of rifampin, a potent inducer of CYP3A4, resulted in a mean decrease in regorafenib AUC of approximately 50%. There are no clinical data evaluating the effect of chronically co-administered CYP3A4 inducers on regorafenib's efficacy. Since there is a possibility of decreased regorafenib efficacy upon chronic co-administration of CYP3A4 inducers with regorafenib, due to the lower plasma concentrations, **chronic co-administration of strong CYP3A4 inducers with regorafenib should be avoided to the extent possible**. (See Appendix 14.8)

In vitro data indicate that regorafenib, as well as its active metabolites M-2, inhibits glucuronidation mediated by uridine diphosphate glucuronosyl transferases UGT1A1 and UGT1A9, whereas M-5 only inhibits UGT1A1 at concentrations that are achieved in vivo at steady state. Administration of regorafenib with a 5 day break prior to administration of irinotecan resulted in humans in an increase of approximately 44% in mean exposure (AUC) of SN 38, a substrate of UGT1A1 and an active metabolite of irinotecan. An increase in mean exposure (AUC) of irinotecan of approximately 28% was also observed. This indicates that co administration of regorafenib may increase systemic exposure to UGT1A1 and UGT1A9 substrates.

Phase II Study of Perindopril and Regorafenib in mCRC (PARICCA)

Administration of regorafenib (160 mg for 14 days) prior to administration of a single dose of rosuvastatin (5 mg), a BCRP substrate, resulted in a 3.9-fold increase in mean exposure (AUC) of rosuvastatin and a 4.6-fold increase in C_{max} . This indicates that co-administration of regorafenib may increase the plasma concentrations of other concomitant BCRP substrates (e.g. methotrexate, fluvastatin, atorvastatin). **Therefore, it is recommended to monitor patients closely for signs and symptoms of increased exposure to BCRP substrates.**

The concentration-time profile indicates that regorafenib and its metabolites may undergo enterohepatic circulation. Co-administration with neomycin, a poorly absorbed antimicrobial agent used for eradicating the gastrointestinal microflora (which may interfere with the enterohepatic circulation of regorafenib) had no effect on the regorafenib exposure. There was an approximately 80% decrease in the exposure of the active metabolites M-2 and M-5. Effects of other antibiotics have not been studied. The clinical significance of the neomycin effect and potential interactions with other antibiotics is unknown, but may result in a decreased efficacy of regorafenib.

The concentration-time profile indicates that regorafenib and its metabolites may undergo enterohepatic circulation. Bile salt-sequestering agents may interact with regorafenib by forming insoluble complexes which may impact absorption (or reabsorption), thus resulting in potentially decreased exposure. The clinical significance of these potential interactions is unknown, but may result in a decreased efficacy of regorafenib.

Co-administration of ACE inhibitors, including COVERSYL[®], with other agents blocking the RAS, such as ARBs or aliskiren-containing drugs, will not be allowed, since such treatment has been associated with an increased incidence of severe hypotension, renal failure, and hyperkalemia.

Caution with use of potassium sparing diuretics

Caution for development of hypotension with diuretics

BSC includes any concomitant medications or treatments: antibiotics, analgesics, radiation therapy for pain control (limited to bone metastases), corticosteroids, transfusions, psychotherapy, growth factors, palliative surgery, or any other symptomatic therapy necessary to provide BSC, except other investigational anti-tumor agents or anti-neoplastic chemotherapy.

Permitted concomitant medications:

- Standard therapies for concurrent medical conditions. Prophylactic anti-emetics may be administered according to standard practice.

Phase II Study of Perindopril and Regorafenib in mCRC (PARICCA)

- Treatment with non-conventional therapies (for example herbs or acupuncture), and vitamin/mineral supplements is acceptable provided that they do not interfere with the study endpoints, in the opinion of the Investigator. St John's wort is not permitted.
- Bisphosphonates
- Patients who are therapeutically treated with an agent such as warfarin or heparin will be allowed to participate provided that no prior evidence of underlying abnormality in coagulation parameters exists. Close monitoring of at least weekly evaluations will be performed until INR/PTT is stable based on a measurement that is pre-dose as defined by the local standard of care.
- Clinical data indicate that regorafenib has no effect on digoxin pharmacokinetics, therefore can be given concomitantly with p-glycoprotein substrates, such as digoxin, without a clinically meaningful drug interaction.

Non-permissible concomitant medications:

- Systemic anticancer therapy including cytotoxic therapy, signal transduction inhibitors, immunotherapy, hormonal therapy and experimental or approved therapies during this trial or within 14 days before starting to receive study medication.
- TKIs
- Bone marrow transplant or stem cell rescue.
- Prior radiation and concomitant palliative radiation therapy is allowed if the target lesion(s) are not included within the radiation field and no more than 10% of the bone marrow is irradiated.
- Use of biologic response modifiers, such as granulocyte colony stimulating factor (G-CSF), within 3 weeks of study entry. G-CSF and other hematopoietic growth factors may be used during the study in the management of acute toxicity such as febrile neutropenia when clinically indicated or at the discretion of the investigator; however they may not be substituted for a required dose reduction. Patients taking chronic erythropoietin are permitted.
- Patients taking narrow therapeutic index medications (e.g., warfarin, phenytoin, quinidine, carbamazepine, Phenobarbital and cyclosporine) should be monitored proactively. Warfarin is metabolized by the cytochrome enzyme CYP2C9 and its levels may be especially affected by regorafenib.

Therapeutic monitoring should be performed consistent with the local clinical standard of care following dose modification of the agent. In general, patients should be closely monitored for side effects of all concomitant medications regardless of path of elimination.

7. Procedures and variables

